7.3 Sample Size Considerations

The sample size for the study of one-hundred and fifty (150) treated participants was established to assure adequate power for the primary safety and effectiveness endpoints as

well as to result in a sufficient sample size (when accounting for attrition) for assessment of the secondary and exploratory endpoints, specifically for those that only apply to subsets of the overall population (i.e. the incident population and wrist arterial procedure access population).

- 1) *Primary Safety Endpoint* The proportion of participants with freedom from device-or procedure-related SAEs through 30 days (ITT Population).
 - Assumptions:
 - The freedom from device- or procedure-related SAE rate for AVFs created using the WavelinQTM EndoAVF System is estimated at 92.6% through 30 days based on pre-market data;
 - The PG is set at 82.6% using a 10% non-inferiority margin;
 - The rate of attrition through 30 days is assumed to be 10%; and
 - o The Type 1 error is 0.05 (two-sided).
 - Sample Size:
 - A sample size of 150 treated participants [135 evaluable] will give over 92.5% power with a two-sided type I error of 0.05 as calculated using PASS 2019 (One Proportion Exact Test).
- 2) Primary Effectiveness Endpoint Interventions Post Creation to Facilitate AVF Use and / or Maintain AVF Use (Facilitation and / or Maintenance Interventions) through the Timepoint of the 6-Month Follow-Up of the Last Active Treated Participant (AT Population)
 - Assumptions:
 - The number of interventions post creation to facilitate AVF use and / or maintain AVF use after AVF creation using the WavelinQTM EndoAVF System is estimated at 3.0 / PY, a conservative assumption based on pre-market data;
 - The PG is set at 5 / PY to align with the targets and recommendations of the 2019 update of the KDOQI Clinical Practice Guideline for Vascular Access of < 2 interventions to facilitate and < 3 interventions to maintain AVF use;
 - The rate of attrition through 6-, 12-, and 24-months, including lost to followup, death, and other clinical investigation premature withdrawals is assumed to be 20%, 40%, and 60%, respectively; and
 - o The Type 1 error is 0.05 (two-sided).
 - Sample Size:
 - O A sample size of 150 treated participants, yielding more than 100 PY by the time the last active treated participant completes their 6-month follow-up, will give over 99% power with a two-sided type I error of 0.05 as calculated using PASS 2019 (One-Sample Poisson Rate Test).

Hence, the sample size of 150 treated participants will provide approximately 92.5%*99%= 91.5% power for the co-primary endpoints.

7.4 Primary Endpoints

7.4.1 Primary Safety Endpoint

The primary safety endpoint is the proportion of AVF with freedom from device-related or procedure-related SAE through 30 days as defined in Section 4.1.1.

7.4.2 Primary Safety Endpoint Hypothesis Test

Objective: To assess if the 30 day primary safety rate endpoint for the WavelinQTM EndoAVF System is greater than the safety PG.

The primary safety endpoint will be evaluated by the following hypothesis:

H₀: The primary safety endpoint of proportion of AVF with freedom from SAE for the WavelinQTM EndoAVF System treated participants through 30 days (Pws) is less than or equal to that of the PG of 82.6%.

H₁: The primary safety endpoint of proportion of AVF with freedom from SAE for the WavelinQTM EndoAVF System treated participants through 30 days (Pws) is greater than that of the PG of 82.6%.

That is:

H₀: Pws \leq 82.6%

 H_1 : $P_{WS} > 82.6\%$

Rejection of the null hypothesis will signify that the 30 day safety of the WavelinQTM EndoAVF System is greater than the safety PG of 82.6%.

The primary safety analysis will be conducted on the ITT population. A two-sided p-value will be derived based on an exact binomial test comparing to the PG of 82.6% and the 95% confidence interval (CI) will be provided. The WavelinQTM EndoAVF System will be considered to have achieved the safety objective and will reject the null hypothesis if the two-sided p-value is less than 0.05, equivalently, the lower bound of the 95% CI is greater than 82.6%.

7.4.3 Primary Effectiveness Endpoint

The primary effectiveness endpoint of the clinical investigation is an effectiveness measure based on the number of interventions post creation to facilitate AVF use and /

or maintain AVF use through the timepoint of the 6-month follow-up of the last active treated participant as defined in Section 4.1.2.

7.4.4 Primary Effectiveness Endpoint Hypothesis Test

Objective: To assess if the number of interventions post creation to facilitate AVF use and / or maintain AVF use (Facilitation and / or Maintenance Interventions) per PY for the WavelinQTM EndoAVF System is less than the PG.

The primary effectiveness endpoint will be evaluated by the following hypothesis:

- **H₀:** The number of interventions post creation to facilitate AVF use and / or maintain AVF use (Facilitation and / or Maintenance Interventions) per PY of participants treated with the WavelinQTM EndoAVF System (RwE) is greater than or equal to that of the PG of 5 post creation facilitation and maintenance interventions / PY.
- **H**₁: The number of interventions post creation to facilitate AVF use and / or maintain AVF use (Facilitation and / or Maintenance Interventions) per PY of participants treated with the WavelinQTM EndoAVF System (RwE) is less than that of the PG of 5 post creation facilitation and maintenance interventions / PY.

That is:

 H_0 : RwE \geq 5 post creation facilitation and maintenance interventions / PY

H₁: Rw_E < 5 post creation facilitation and maintenance interventions / PY

Rejection of the null hypothesis will signify that the number of interventions post creation to facilitate AVF use and / or maintain AVF use (Facilitation and / or Maintenance Interventions) per PY of AVFs created using the WavelinQTM EndoAVF System is less than the PG of 5 post creation facilitation and maintenance interventions / PY.

The primary effectiveness analysis will be conducted on the AT population after the last active treated participant completes their 6-month follow-up; by this time, all participants still in the clinical investigation will have at least 6-months of data. The number of Facilitation and / or Maintenance Interventions per PY will be estimated by Poisson regression model with only the intercept term, and the estimate and 95% CI will be provided, and the p-value comparing to the PG will be calculated by a chi-square test.

7.5 Secondary Endpoints

The secondary endpoints will be summarized with descriptive statistics (without formal statistical hypothesis testing) using the ITT population for the safety endpoints and the AT population for the effectiveness endpoints. For time-to-event endpoints, the KM production limit method will be used to determine the rate. For categorical variables, summary statistics will include frequency counts and percentages. For rate variables, summary statistics including number of event / PY. For continuous variables, summary statistics will include mean, standard deviation, minimum, median, and maximum. CIs (95%) will be provided using appropriate assumptions based on the variable type. Refer to Section 4.2 for any applicable definitions.

7.5.1 Safety

• Device- and Procedure-Related SAEs evaluated through 6- and 24-months.

7.5.2 Effectiveness

- Physiological Maturation evaluated through 6-weeks.
- Cannulation Success assessed through 6-months.
- Cumulative Functional Patency evaluated through 12-months.

7.6 Exploratory Endpoints

The exploratory endpoints may or may not be presented in the clinical investigation report. If reported, the descriptive statistics will be presented.

7.7 General Considerations

7.7.1 Subgroup Analyses

Primary and secondary endpoints may be explored by subgroup, including but not limited to:

- Sex;
- Age;
- Site of anastomosis (ulnar-ulnar; radial-radial; other); and
- Location of arterial procedure access (wrist; upper arm).

A full list of subgroups will be detailed in the Statistical Analysis Plan, which will be approved prior to database lock. The subgroup analyses will be summarized using descriptive statistics.

7.7.2 Poolability Analysis by Geographical Region and Investigational Site

A poolability analysis by geographical region and by investigational sites will be performed on the primary endpoints. Sites with less than 10 treated participants will be pooled by site number to form combined site(s) with at least 10 treated participants.

7.7.3 Handling of Missing Data

Investigation endpoints may have missing data due to a participant's withdrawal of consent, the withdrawal of a participant by the PI, a participant loss to follow-up and the death of a participant. Data may also be missing from investigation endpoints due to deviations and / or missing data collection. It is important to minimize missing data by all means and to always record the reason for omission.

For the primary safety endpoint, a conservative approach will be used for the handling of missing data: If a participant has a specified event (device-related or procedure-related SAE), the participant will be included irrespective of if the participant prematurely discontinues prior to the 30 day timepoint; if a participant prematurely discontinues before 30 days without the occurrence of a specified event, the participant will be considered not evaluable and will not be included in the primary safety endpoint analysis.

For the primary effectiveness endpoint, the Poisson regression model will be used to analyze the data. In the Poisson regression model, missing data handling is a standard part of the analysis: If a treated participant prematurely discontinues prior to the data cut, that participant's study duration will be considered as the period of time between the index procedure and their premature discontinuation, and the corresponding number of facilitation and/or maintenance interventions in that specific duration will be used for analysis.

7.8 Analysis Timing

The primary reporting will occur when the last active treated participant has completed their 6-month follow-up. A final analysis will be completed when all participants have completed, or prematurely discontinued before, their 24-month follow-up. Note that to support regulatory submissions in the U.S. pertaining to the procedure access at the wrist arteries exploratory endpoint and ad-hoc analyses may be conducted at intervals other than those defined in this section looking specifically at data pertaining to arterial procedure access at the wrist.

8 SAFETY MONITORING AND REPORTING

The PI is responsible for the detection, documentation and reporting of events and any new information concerning reported events to the Sponsor that meet the criteria and definitions set forth in this section. These events will be collected for ITT participants and collection thereof will begin immediately following the start of the index procedure (defined to start at the time of the initial skin puncture to gain vessel access). Events occurring prior to the index procedure, will be documented as medical history. Events and the status thereof will be collected through the final investigation required participant follow-up visit or premature discontinuation.

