Participants into whom the WavelinQTM EndoAVF System was not introduced should be treated per SOC and the reason documented on the appropriate eCRF. Participation for these participants will end at time of the index procedure.

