6.3 Post-Index Procedure and Discharge

Medication therapy and medical treatment will be conducted at the discretion of the PI per the investigational site's SOC. Participants will be treated and discharged according to the site's SOC. Prior to discharge, the following data will be collected and documented on the appropriate eCRF for participants into whom the WavelinQTM EndoAVF system was introduced:

- Clinical Exam: Overall health and assessment of AV access function must be evaluated and documented with a physical exam conducted by the PI or authorized designee in accordance with each investigational site's SOC.
- Documentation of Adverse Events (AEs): Documentation of AEs (refer to Section 8) that have occurred since the start of the index procedure (defined to begin at the time of the initial skin puncture to gain vessel access).
- Documentation of Interventions: Any access circuit interventions the participant has undergone since the completion of the index procedure (defined to end at the time of last sheath removal start of access site closure).

Note that for participants into whom the WavelinQTM EndoAVF System was introduced but procedure success was not achieved, the clinical exam at discharge will review the health and assessment of the vessels interacted with during the index procedure. These vessels should also be imaged prior to discharge to confirm the absence of any AEs.

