7.2 Analysis Populations

The analysis populations will be defined as follows:

- The ITT population will consist of all participants into whom the WavelinQTM Endovascular System was introduced including those in whom procedure success was not achieved.
- An As-Treated (AT) population will include all treated participants, which includes all ITT participants but excludes those into whom the WavelinQTM Endovascular System was introduced but procedure success was not achieved.
 - The AT population is composed of two subpopulations: The incident population and the prevalent population as defined in Section 4.5.2.
- A Per-Protocol (PP) population may be created if there are participants who have any major deviations. The PP population will consist of any participants in the AT population who do not have any major deviations. The deviations that are considered to have a "major" grade will be defined a priori in the SAP.

All effectiveness endpoints will be analyzed primarily based on the AT population. All safety endpoints will be analyzed primarily based on the ITT population. PP analyses may also be performed for the primary endpoints. They will only serve as sensitivity analyses for the primary analyses.

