Risks associated with sedation and / or anesthesia	These risks can include: Nausea Vomiting Hematoma at injection site Sore throat / hoarse voice Damage to teeth Brain damage Death These risks can include:	 As delineated in Section 12.1 the PI as well as any additional operators (as applicable) must be experienced in the field of application. Clinical Eligibility Criteria must be met and documented using prior to treatment including assessment of the participants eligibility to receive sedation and / or anesthesia (Section 5.1). The CIP required follow-up ensures close participant monitoring for AEs throughout the course of the investigation (Section 6.4). As delineated in Section 12.1 the PI 			
angiography	Kidney damage Allergic reaction	 as well as any additional operators (as applicable) must be experienced in the field of application. Clinical Eligibility Criteria must be met and documented using prior to treatment including assessment of the participants eligibility to receive contrast media (Section 5.1). The CIP required follow-up ensures close participant monitoring for AEs throughout the course of the investigation (Section 6.4). 			
Risks associated with vessel embolization placement, if completed.	These risks can include: Allergic reaction Hemolysis Migration Occlusion of unintended vessel Recanalization Stroke Tissue ischemia Vessel trauma including perforation, rupture, or extravasation Others, as delineated in the embolization device labeling and IFU	 As delineated in Section 12.1 the PI as well as any additional operators (as applicable) must be experienced in the field of application. The CIP required follow-up ensures close participant monitoring for AEs throughout the course of the investigation (Section 6.4). 			

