	Not involved in the development of the investigation device or the
Independent	conduct of a clinical investigation, except for their specifically
писреписи	assigned responsibilities, in order to avoid bias or a conflict of
	interest.
Index AVF / AV Access	The index AVF / AV access circuit refers to the AVF / AV access
Circuit	circuit originally created as part of this clinical investigation at the
	time of the index procedure.
	The procedure intended to create the investigation AVF (index AVF)
Index Procedure	using the WavelinQ TM EndoAVF System defined to begin at the time
index Procedure	of the initial skin puncture to gain vessel access and end at the time
	of last sheath removal (start of access site closure).

Term	Definition
Infiltration Injury ⁸	 A vessel injury related to cannulation or the dialysis procedure and can be categorized as below: Minor cannulation injury – an injury that may result in bleeding infiltration and swelling that may be treated with conservative measures such as ice and rest for 1-2 days but cannulation can be re-attempted for the next dialysis session. The access should be successfully re-cannulated with 2 needles in < 7 days. Note that even a minor cannulation injury may require the use of a temporary catheter. Major cannulation injury – an injury that results in significant bleeding infiltration and swelling that requires recovery for >7 days. Severe cannulation injury – an injury that results in significant bleeding complications that requires one of: blood transfusion, emergency room visit, hospitalization, radiological or surgical intervention.
Informed Consent	Process by which an individual voluntarily confirms willingness to participate in a particular clinical investigation, after having been informed of all aspects of the investigation that are relevant for the decision to participate.
Intent to Treat (ITT) Population	All treated participants including those for whom RF energy was not administered but the WavelinQ TM Endovascular System was introduced.

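### A serious complication between skin puncture and device introduction that aborts the case meets the primary safety event definition but falls outside required adverse event collection and the analysis set

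*Protocol*

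**What the plan says.** **Collection.** Protocol Section 8 sets both who is covered and from when: "These events will be collected for ITT participants and collection thereof will begin immediately following the start of the index procedure". Section 6.3 places the start of the index procedure early; it is "defined to begin at the time of the initial skin puncture to gain vessel access".

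**Population.** Protocol Section 7.2 ties ITT to a later step: "The ITT population will consist of all participants into whom the WavelinQTM Endovascular System was introduced". SAP Section 4.1 agrees. Protocol Appendix B words ITT differently ("All treated participants including those for whom RF energy was not administered but the" device was introduced), but it also requires introduction.

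**Follow-up.** For participants in whom the device was not introduced, Section 6.2.1 asks only for the reason and then states: "Participation for these participants will end at time of the index procedure". SAP Section 2.6 repeats this. Pre-discharge adverse event data in Section 6.3 are likewise limited to participants with device introduction. By contrast, participants with introduction but no procedure success are followed to 30 days, by phone if necessary (Section 6.4.1).

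**Endpoint.** The primary safety endpoint counts CEC-adjudicated device- or procedure-related SAEs through 30 days (Section 4.1.1). Section 8.3 treats an event as procedure-related if it is directly attributable to the index procedure. The analysis set is ITT (protocol Section 7.4.2), restricted to evaluable participants in SAP Section 5.1.1.

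**The concern.** Collection opens at puncture, but it applies only to people defined by something that happens after puncture. Between the two lies the access phase, in which a bleed, an arterial injury or a contrast reaction can occur. If such an event is serious and makes the operator stop, the participant never enters ITT. Whether that participant is counted then depends on the outcome being measured, which is the kind of exclusion a safety endpoint should avoid.

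Two things are at stake. The primary safety proportion describes only participants who got through the access phase. And those harmed in that phase have no study safety contact, although Table 3 in Section 9.1 lists study follow-up among its mitigations for, for example, "Risks associated with sedation and / or anesthesia".

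**Working it through.** **1. Tracing one participant through the rules.** Suppose a participant is punctured, has a serious arterial injury, and the case is stopped before the catheters go in.

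- Index procedure started: yes (Section 6.3).
- Procedure-related under Section 8.3: it can be, since the injury is attributable to a procedure already under way.
- Member of ITT: no, because the device was not introduced (protocol 7.2, SAP 4.1).
- Covered by the collection rule in Section 8: no, because it is limited to ITT.
- 30-day contact: none (Section 6.2.1).
- In the primary safety denominator: no (protocol 7.4.2, SAP 5.1.1).

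The rule in Section 7.7.3 that keeps early discontinuers who had an event does not help, because the analysis it serves is confined to ITT.

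**2. Reproducing the plan's figure.** Inputs from protocol Section 7.3: expected event-free rate 92.6%, performance goal 82.6%, two-sided alpha 0.05, 150 treated, 10% attrition, so 150 × 0.90 = 135 evaluable. Rule: pass if the Clopper-Pearson 95% lower bound exceeds 82.6%. At n = 135 this needs at least 121 event-free, so at most 14 events (lower bound 83.2%). Power = P(X ≥ 121 | n = 135, p = 0.926) = 0.925, which matches the stated figure.

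Section 3 expects about 10 further participants with introduction but no success, so ITT is about 160, or 160 × 0.90 = 144 evaluable. There the limit is 15 events (129/144 event-free, lower bound 83.4%) and power is 0.932.

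**3. Adding omitted failures to a result that only just passes.** The number of aborted cases is not in the documents; k below is an assumption. Each added participant is a failure and no event-free aborted case is added.

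| Base | k | Events / n | Lower bound | Result |
|---|---|---|---|---|
| 135 | 0 | 14/135 | 83.2% | pass |
| 135 | 1 | 15/136 | 82.5% | fail |
| 144 | 0 | 15/144 | 83.4% | pass |
| 144 | 1 | 16/145 | 82.7% | pass |
| 144 | 2 | 17/146 | 82.0% | fail |

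**4. Adding one failure together with event-free aborted cases.** From the 135 base with 14 events, assume 2 to 5 aborted cases of which one had an SAE:

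- 2 aborted: 15/137, lower bound 82.585%, fail by a very small margin.
- 3 aborted: 15/138, 82.71%, pass.
- 4 aborted: 15/139, 82.83%, pass.
- 5 aborted: 15/140, 82.94%, pass.

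From the 144 base with 15 events, 2 aborted cases with one SAE give 16/146, 82.81%, pass.

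**5. How often a result would be that close.** At 92.6% the expected number of events among 135 is 135 × 0.074 = 10.0. The probability of exactly 14 is about 5%.

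**6. Chance of success when omitted failures are counted.** With a 92.6% rate among device-introduced participants and failures only added, it is 92.5% (k = 0), 87.4% (k = 1) and 80.0% (k = 2) at base 135, and 93.2%, 93.2% and 88.6% at base 144. These show the largest effect for each k, because no event-free aborted case is credited.

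**The case against.** **The documents are not silent on these events.** The Schedule of Activities marks adverse event assessment at the index procedure, Section 8.4 says all adverse events should be recorded promptly, Section 8.5 requires every death to be reported, and Section 8.6 applies adverse event reporting to device deficiencies where insertion was attempted. A reader might infer from Section 8 that an aborted case leaves no adverse event record at all. That goes too far: some such events may reach the sponsor. What remains is that these passages conflict with the limit in Section 8, and none of them puts the participant into ITT or creates a 30-day contact.

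**The direction is not fixed.** A reader might infer that the exclusion always favours the device. Leaving out the harmed participants does. But Section 6.2.1 recommends rechecking anatomical eligibility at the index procedure, so some cases may be aborted after puncture for anatomy alone. Counting every punctured participant would add those event-free cases too, and the net change could be smaller or even reversed.

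**Table 3 does not rest on follow-up alone.** For sedation and contrast it also lists operator experience and eligibility screening. Follow-up is one of three mitigations.

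**Events before puncture follow a different rule.** Section 8 says "Events occurring prior to the index procedure, will be documented as medical history". A sedation event before puncture is therefore medical history even in someone who later receives the device. This is consistent with the stated start of the procedure; counting it would change the endpoint.

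**The primary population has a rationale.** The hypotheses in Section 7.4.2 concern treated participants, and the 82.6% goal comes from earlier studies whose denominator is not shown. Replacing ITT for the primary test could break comparability with that goal. This argument stands, and it supports a sensitivity analysis in place of a new primary set.

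**Conclusion.** The gap is real and follows from the plan's own definitions: a procedure-related SAE between puncture and device introduction that aborts the case is an endpoint event by definition, but it is outside required collection and the primary safety set. The exclusion depends on the outcome.

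Its size is unknown, because no count of aborted cases is given, and it is probably small. Only a borderline result could change. One omitted failure added alone is enough at 135 evaluable; two are needed at 144. It would be wrong to conclude that a single such SAE generally reverses the result: with one SAE among 3 to 5 aborted cases at the 135 base, or among 2 at the 144 base, the borderline pass survives. The stated power of over 92.5% is reproduced and is not in dispute.

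The Appendix B wording is a separate drafting inconsistency. It speaks of treated participants plus those for whom RF energy "was not administered but the WavelinQ TM Endovascular System was introduced"; read literally, it does not name participants who received RF energy without procedure success, whom Section 7.2 and SAP Section 4.1 include.

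**What to change.** - **Protocol Sections 6.2.1, 6.3, 6.4.1 and 8, and SAP Section 2.6:** collect adverse events from skin puncture in every participant in whom the index procedure was started, whether or not the device was introduced. Extend to them the 30-day phone safety contact already used when procedure success is not achieved.
- **SAP Section 5.1.1:** keep the device-introduced ITT set for the primary test. Add a prespecified sensitivity analysis of the primary safety endpoint in all punctured participants, and report how many were aborted before introduction and how many of those had a procedure-related SAE.
- **Protocol Appendix B:** align the ITT definition with protocol Section 7.2 and SAP Section 4.1.

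The cost is amendment wording, one phone call and an adverse event page for what is likely to be a few participants, and a sensitivity result that may be slightly less favourable. The As-Treated population and the effectiveness analysis are unaffected. The change is best made while participants are still being treated, since these data are hard to recover once participation has ended.
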